7.7 SAFETY ANALYSES

This study involves data that exist as structured data by the time of study start. In these data sources, individual patient data are not retrieved or validated, and it is not possible to link (i.e., identify a potential association between) a particular product and medical event for any individual. Thus, the minimum criteria for reporting an adverse event (AE) (i.e., identifiable patient, identifiable reporter, a suspect product, and event) cannot be met.

PFIZER CONFIDENTIAL

CT24-WI-GL03-RF03 2.0 Non-Interventional Statistical Analysis Plan For Secondary Data Collection Study
01-Jun-2020
Page 22 of 29

9 APPENDICES

9.1 APPENDIX 1: RULES FOR DEFINING CHANGE IN THERAPY LINE

Condition	Rule
Switch to a completely new agent or combination of agents	Change in therapy line
Switching between CDK4/6 inhibitors (e.g., palbociclib to ribociclib or abemaciclib)	Change in therapy line
Therapy suspended for greater than 90 days	Change in therapy line
Addition of a new agent to an existing treatment regimen*	Change in therapy line
Removal of an agent from a combination regimen	Not a change in therapy line
Exception to switching within the same treatment class	
Anastrozole to letrozole (or vice versa)	Not a change in therapy line
Anastrozole to exemestane (or vice versa)	Not a change in therapy line
Letrozole to exemestane (or vice versa)	Not a change in therapy line

CDK4/6 = cyclin-dependent kinase 4 and 6.

** A treatment regimen is defined as combination of all agents administered within a 30-day period from the date of initiation of the first agent, with the exception of CDK4/6 inhibitors, for which a 60-day period will be allowed to account for insurance coverage delays. Addition of a new agent after 30 days (or 60 days for CDK4/6 inhibitors) will be considered a change in therapy line. A given therapy line will be considered to have ended upon occurrence of the earliest of any of the following: switch to a new treatment regimen or a gap of more than 90 days in administration or refill of any of the first line regimen drugs.*

9.2 APPENDIX 2: LIST OF SYSTEMIC THERAPY AGENTS

Therapy agents	HCPCS codes
CDK4/6 inhibitors	
Palbociclib	N/A
Ribociclib	N/A
Abemaciclib	N/A
Aromatase inhibitors	
Anastrozole	S0170
Letrozole	N/A
Exemestane	S0156
Other hormonal therapy	
Fulvestrant	J9393, J9394, J9395, C9120
Tamoxifen	S0187
Toremifene	N/A
Kinase inhibitor	
Everolimus	J7527, J8561
Specific chemotherapy agents	
Doxorubicin (all forms)	C9415, J9000, J9001, J9002, Q2048, Q2049, Q2050
Epirubicin	C1167, J9178, J9180
Eribulin	C9280, J9179
Gemcitabine	J9198, J9201
Capecitabine	J8520, J8521
Docetaxel	J9170, J9171
Paclitaxel (all forms)	C9127, C9431, J9264, J9265, J9267, J9259
Cyclophosphamide	C9420, C9087, C9421, J8530, J9070, J9071, J9080, J9090, J9091, J9092, J9093, J9094, J9095, J9096, J9097
Fluorouracil	J9190
Cisplatin	C9418, J9060, J9062
Carboplatin	J9045
Oxaliplatin	C9205, J9263
Methotrexate	J8610, J9250, J9260
Vinorelbine	C9440, J9390
Vinblastine	J9360

PFIZER CONFIDENTIAL

CT24-WI-GL03-RF03 2.0 Non-Interventional Statistical Analysis Plan For Secondary Data Collection Study
 01-Jun-2020
 Page 28 of 29

Therapy agents	HCPCS codes
Leuprolide	C9430, J1950, J9217, J9218, J9219, J1952
Irinotecan	C9474, J9205, J9206
Ixabepilone	C9240, J9207
Etoposide	C9414, C9425, J8560, J9181, J9182
Mitomycin	C9432, J9280, J9290, J9291, J9281, C9064
NOS chemotherapy agent	J8999, J9999
Other targeted therapies	
Olaparib	N/A
Alpelisib	N/A
Lapatinib	N/A
Tucatinib	N/A
Neratinib	N/A
Larotrectinib	N/A
Entrectinib	N/A
Talazoparib	N/A
Trastuzumab (all forms)	C9131, J9316, J9354, J9355, J9356, J9358, Q5112, Q5113, Q5114, Q5116, Q5117
Pertuzumab	C9292, J9306, J9316
Bevacizumab	Q2024, C9257, C9214, Q5118, Q5107, C9142, Q5126, Q5129, S0116, J9035
Pembrolizumab	C9027, J9271
Atezolizumab	C9483, J9022
Sacituzumab	C9066, J9317
Nivolumab	C9453, J9299, J9298

CDK4/6 = cyclin-dependent kinase 4 and 6; HCPCS = Healthcare Common Procedure Coding System; N/A = not available; NOS = not otherwise specified.

Note: All treatments will be identified using a combination of HCPCS codes and the generic drug names in the Medicare Prescription Drug Event file that are linked to corresponding National Drug Codes assigned to each drug. Treatments with no applicable HCPCS codes will only be identified using generic drug names.

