5.4 STUDY ENDPOINTS

The endpoints or study outcomes to be analyzed for each study objective and the associated definitions are described in [Table 5-1](#).

Table 5-1. Definition of Endpoints

Variable	Role/objective	Definition
Overall survival in 1L	Primary	The time in months from initiation of 1L therapy (palbociclib + AI or AI alone) to all-cause death . Patients who did not die will be censored at the end of study follow-up as defined in Section 2.1 .
CCI		[REDACTED]

Variable	Role/objective	Definition
CCI		
Time to chemotherapy	Exploratory	Time in months from the study index date to first initiation of chemotherapy in any subsequent therapy lines. Patients who did not initiate chemotherapy treatment as of last follow-up will be censored at the end of the follow-up.

1L = first line; AI = aromatase inhibitor; CDK4/6 = cyclin-dependent kinase 4 and 6;

CCI

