Metastatic site involvement at diagnosis	Clinical characteristic (assessed at mBC diagnosis)	The SEER-defined metastatic site variables will be used to describe involvement of any of the following sites at diagnosis: 
 • Bone • Brain • Liver • Lung • An additional variable will be created to describe presence of visceral metastases using the composite of liver and lung.
NCI Comorbidity Index (NCICI) Score	Clinical characteristic (assessed within the 6 months period before index date)	The comorbidity burden during the 6-month baseline period will be assessed using the NCI's comorbidity index, which is described in the Klabunde adaptation of the Charlson Comorbidity Index, version 2021 (Klabunde et al., 2007; National Cancer Institute, 2023a). NCICI scores will be reported as continuous and categorical variables: 
 • Score 0 • $0 < \text{Score} \leq 1$ • $\text{Score} > 1$

PFIZER CONFIDENTIAL

CT24-WI-GL03-RF03 2.0 Non-Interventional Statistical Analysis Plan For Secondary Data Collection Study
 01-Jun-2020
 Page 13 of 29

Variable	Role/objective	Definition
		
The specific comorbidities represented in the NCICI include the following:
 
 • Acute myocardial infarction • History of myocardial infarction • Congestive heart failure • Peripheral vascular disease • Cerebrovascular disease • Chronic obstructive pulmonary disease • Dementia • Paralysis (hemiplegia or paraplegia) • Diabetes without complications • Diabetes with complications • Renal disease • Mild liver disease • Moderate/severe liver disease • Peptic ulcer disease • Rheumatologic disease • AIDS
Age	Demographics (assessed at mBC diagnosis and at index date)	
Age at diagnosis will be assessed as continuous and categorical variables:
 
 • 65-69 years • 70-74 years • 75-79 years • ≥ 80 years
Year of diagnosis	Demographics (assessed at mBC diagnosis)	
Year of de novo mBC diagnosis will be described as a categorical variable:
 
 • 2015 • 2016 • 2017 • 2018 • 2019

PFIZER CONFIDENTIAL

Variable	Role/objective	Definition

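### The agent list files leuprolide as chemotherapy and sets no form or indication limit on Part D matches for methotrexate and fluorouracil, so non-chemotherapy fills can be read as chemotherapy

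*SAP*

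**What the plan says.** The agent table is the same in SAP section 9.2 (Appendix 2) and protocol Annex 2 (List of Systemic Therapy Agents). Under the heading "Specific chemotherapy agents", between vinblastine and irinotecan, stands leuprolide with the codes "C9430, J1950, J9217, J9218, J9219, J1952". The separate group "Other hormonal therapy" holds only fulvestrant, tamoxifen and toremifene. Methotrexate ("J8610, J9250, J9260") and fluorouracil (J9190) are also under the chemotherapy heading.

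The note to the table gives the matching rule: "All treatments will be identified using a combination of HCPCS codes and the generic drug names in the Medicare Prescription Drug Event file". It adds that these names are linked to National Drug Codes, and it ends: "Treatments with no applicable HCPCS codes will only be identified using generic drug names".

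Three other rules use these classifications:

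- SAP Table 5-1 defines time to chemotherapy as the time from index to "first initiation of chemotherapy in any subsequent therapy lines".
- SAP Table 5-2 defines first line as every agent given within 60 days of treatment start, and SAP section 4.1 (criterion 6) restricts the cohort to palbociclib + AI or AI alone.
- SAP Appendix 1 treats the addition of a new agent as a change of line.

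**The concern.** Leuprolide suppresses hormones and is not cytotoxic, so its place in the table looks like a filing error with a consequence: a leuprolide fill or administration in a later line would be scored as the start of chemotherapy. The study includes men as well as women (SAP section 2.2), so its use cannot be assumed absent.

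Methotrexate and fluorouracil raise a different problem. Both have uses outside oncology, such as methotrexate for a rheumatologic disease or fluorouracil as a topical product. The documents do not discuss these uses, but the SAP's own comorbidity list includes "Rheumatologic disease", and no eligibility criterion excludes such patients. If a Part D fill is caught on its name, nothing in the visible rules separates it from cancer chemotherapy.

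At stake are false events in an exploratory endpoint and, for a fill near the start of the AI, a wrong regimen label at cohort entry.

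**Working it through.** The plan attaches no figure to this point (protocol section 9.5 states that no formal sample size estimation was done), so there is nothing to reproduce. The check is mainly a reading of the rules together.

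**1. Leuprolide.** No new heading comes between "Specific chemotherapy agents" and the targeted therapies, so the row belongs to the chemotherapy group in both documents. This is the only chemotherapy list shown. Combined with Table 5-1, a later-line leuprolide claim is an event.

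**2. How the two sources combine.** The note does not say whether a match needs both sources or either one. Requiring both would break the exposure definition. Anastrozole (S0170) and exemestane (S0156) carry HCPCS codes, yet Table 5-2 looks for first-line treatment in the Prescription Drug Event file by generic name, and by HCPCS code as applicable. An ordinary Part D fill of either drug, recorded by name, would then be missed. The workable reading is that either source suffices. On that reading a Part D fill of methotrexate or fluorouracil is captured by name, and no visible rule limits form, route, dose or indication.

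**3. What follows from such a fill.** In a later line it is a time-to-chemotherapy event. Within the first-line window it adds an agent, and the regimen is then neither palbociclib + AI nor AI alone. (Table 5-2 counts all agents within 60 days; the Appendix 1 footnote allows 30 days for agents other than CDK4/6 inhibitors. Which rule catches a fill between day 31 and day 60 is therefore itself unclear.)

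**4. Does re-heading leuprolide alter cohort entry?** No. First line is defined by all agents, whatever their heading. Read literally, AI + leuprolide is not AI alone under either heading.

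**5. Size, by assumption only.** Suppose false events arise at the same constant monthly rate *h* in both arms, with assumed true hazards of 0.0084 and 0.012 (ratio 0.0084/0.012 = 0.70). The observed ratio is (0.0084 + *h*)/(0.012 + *h*):

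- *h* = 0.0005: 0.0089/0.0125 = 0.712
- *h* = 0.001: 0.0094/0.0130 = 0.723

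Equivalently, if a share *f* of the AI-alone events is false, the observed HR is HR × (1 − *f*) + *f*. To two decimals:

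| True HR | *f* = 2% | 5% | 10% | 20% |
|---|---|---|---|---|
| 0.60 | 0.61 | 0.62 | 0.64 | 0.68 |
| 0.75 | 0.76 | 0.76 | 0.78 | 0.80 |
| 0.90 | 0.90 | 0.91 | 0.91 | 0.92 |

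False events that are equally frequent in both arms pull the ratio toward 1, and the pull is small unless they are common.

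**The case against.** The strongest reply is that little depends on this. Time to chemotherapy is exploratory and is measured only if follow-up allows. Its definition does not cite Appendix 2, and the exploratory methods in SAP section 7.4 are blacked out, so a narrower chemotherapy rule may exist there. Primary overall survival is all-cause death, analysed regardless of later treatment, so errors in later lines do not touch it. Protocol section 9.9 already concedes some misclassification from the claims algorithm. Link to National Drug Codes may also mean that unsuitable products are dropped in practice. All of this stands as a limit on importance. It does not correct a misplaced row, and a general caveat does not supply the missing matching rule.

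A reader might also infer more than the documents support:

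- *That methotrexate and fluorouracil are matched on name only.* They are not. Both have HCPCS codes, and the note keeps name-only matching for agents without codes. The gap is that a name match in Part D is an additional, unrestricted route.
- *That patients are shown to be lost from the cohort.* The documents give no frequency of such fills, so no share of excluded patients can be stated. Loss is possible, not demonstrated.
- *That moving leuprolide restores patients to the cohort.* It does not (step 4 of the working).
- *That the overall survival hazard ratio is biased.* Nothing shows that any loss would differ between the arms.

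**Conclusion.** The point holds as a minor, correctable fault. Leuprolide is under the wrong heading in both documents, and under the only chemotherapy list shown a later-line claim is a false event. For methotrexate and fluorouracil the fault is an unstated restriction: on the reading that makes the exposure definition work, a non-oncology Part D fill can be taken as chemotherapy.

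The effect is probably small. Under the assumed hazards a ratio of 0.70 moves to 0.71 or 0.72; only when a fifth of the AI-alone events are false does a ratio of 0.60 become 0.68. These figures assume equal false-event rates in both arms and constant hazards, and none of their inputs comes from the documents. The effect acts mainly on the exploratory endpoint and reaches primary overall survival only through cohort classification. The classification of leuprolide as hormonal, and the non-oncology uses of the other two drugs, are general pharmacology and not statements in the plan.

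**What to change.** Make these edits in SAP Appendix 2 and protocol Annex 2, with matching text in the first-line and time-to-chemotherapy definitions, before the final analysis:

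1. Move leuprolide to "Other hormonal therapy" in both tables. State separately how AI + leuprolide is classified in the first-line definition, since the move alone leaves cohort entry unchanged.
2. State in the note that a match in either source suffices.
3. Exclude topical fluorouracil products from Part D matches, using the dosage form attached to the National Drug Code.
4. In the main time-to-chemotherapy and first-line rules, do not count Part D oral methotrexate as chemotherapy when a rheumatologic diagnosis is coded in the baseline period. Add a check that does count it.

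The methotrexate rule should not rely on fills before diagnosis. Criterion 7 requires Part D coverage only from diagnosis to the start of first line, and criterion 8 requires only Parts A and B in the six months before index, so earlier fills may not be visible. Baseline diagnosis codes come from the Parts A and B claims that criterion 8 secures.

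The cost is an edit to the code list, a filter on dosage form and one extra run, with no new data. The downside is that a few true methotrexate chemotherapy events may be missed, and the check in item 4 shows how many are in question.
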